Phase II Trial of Lumpectomy and Partial
Breast Proton Therapy for Early Stage Breast
Cancer

NCT00614172

April 8, 2008

Radiation Medicine Proton Therapy

RMPT 0301

Phase II Trial of Lumpectomy and Partial Breast Proton Therapy for Early Stage Breast Cancer

Loma Linda University Medical Center
Department of Radiation Medicine

Principal Investigators	[name] MD [name] MD
Radiation Medicine	[name] MD
Clinical Physics	[name] PhD
Surgical Oncology	[name] MD
Medical Oncology	[name] MD
Data Management	[name] [name] Radiation Medicine

Revised April 8, 2008

Index

Schema

- 1.0 Introduction
- 2.0 Objectives
- 3.0 Eligibility Criteria
- 4.0 Pretreatment Evaluation
- 5.0 Radiation Therapy
- 6.0 Surgical Therapy
- 7.0 Systemic Therapy
- 8.0 Patient Assessments
- 9.0 Statistics and Data Management

Radiation Medicine Proton Therapy

RMPT – 0301

Phase II Trial of Lumpectomy and Partial Breast Proton Therapy for Early Stage Breast Cancer

Schema

Surgery

Lumpectomy and axillary dissection or sentinel lymph node biopsy.

Proton Therapy

Proton therapy to tumor bed.
Dose = 40 CGE in 10 fractions.

Systemic Therapy

Chemotherapy and/or hormonal therapy as needed per treating oncologist.

Eligibility (see section 3.0 for details)

- Invasive ductal, medullary, papillary, colloid or tubular histologies or ductal carcinoma in-situ (DCIS)
- Stages Tis, T1 or T2 (tumors < or = 3 cm)
- Negative surgical margins (>2mm)
- Negative sentinel node biopsy or three or fewer histologically involved axillary nodes on axillary node dissection. No extra-capsular extension
- No previous chemotherapy for breast cancer
- No collagen vascular disease
- No prior malignancy except non-melanoma skin cancer (unless disease free > 5 years)
- No patients who are pregnant or lactating

Sample Size: 50 patients

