3.0 Eligibility Criteria

- 3.1 Histologic evidence of invasive carcinoma (except lobular carcinoma) or ductal carcinoma-in-situ.
- 3.2 Primary tumor < or = 3 cm.
- 3.3 AJCC stage 0, I, or II
- 3.4 Patients with invasive carcinoma must have an axillary node dissection or sentinel lymph node biopsy. If the sentinel node is positive an axillary node dissection must be performed. A minimum of 6 nodes must be pathologically reviewed. No more than 3 nodes may contain metastatic carcinoma and there can be no evidence of extra-capsular extension. Axillary staging is not required for DCIS.
- 3.5 Surgical clips will be placed outlining margins of lumpectomy cavity.

- 3.6 Lumpectomy margins negative by at least 2 mm and/or negative reexcision
- 3.7 No evidence of distant metastasis.
- 3.8 No evidence of extensive intraductal component.
- 3.9 No patients with multicentric ipsilateral carcinoma or contralateral carcinoma.
- 3.10 No prior radiation therapy to the breast or chest wall.
- 3.11 No prior malignancy except non-melanoma skin cancer unless disease free for > 5 years.
- 3.12 No patients who are pregnant or lactating.
- 3.13 No patients with history of collagen vascular disease.
- 3.14 No prior chemotherapy for breast cancer

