9.0 Statistics and Data Management

9.1 Initially 25 subjects will be enrolled into this trial. After a toxicity evaluation is completed and felt to be acceptable, 25 additional subjects will be enrolled for a total of 50 subjects.

An additional 50 subjects will be enrolled under the new eligibility criteria defined in the April 4, 2008 revision.

9.2 All acute toxicities will be scored according to the NCI Common Toxicity Criteria v2.0. Late toxicity will be scored per RTOG guidelines. Any toxicities with a threshold of Grade 3 or above will be reported as an adverse event. Frequencies of toxicities will be tabulated and compared to published reports.

9.3 Frequency and type of recurrence (local, regional, distant) will be tabulated and compared to prior studies.

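### The schema gives the sample size as 50, but section 9.1 of the same revision plans for 100

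*Combined protocol and SAP*

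**What the plan says.** The schema at the front of the protocol closes with the line "Sample Size: 50 patients". Nothing attached to it mentions a stage, a cohort or section 9.1.

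Section 9.1 sets enrolment in three blocks:

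- first block: "Initially 25 subjects will be enrolled into this trial";
- second block, conditional on an acceptable toxicity evaluation: "25 additional subjects will be enrolled for a total of 50 subjects";
- third block: "An additional 50 subjects will be enrolled under the new eligibility criteria defined in the April 4, 2008 revision".

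Section 9.1 does not print an overall total. The schema's eligibility list refers the reader to section 3.0, which holds a single set of criteria that is not identified as original or revised. The cover page dates the document April 8, 2008, so the schema and section 9.1 belong to the same current version.

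The analysis text does not mention the two cohorts. Section 9.2 says "Frequencies of toxicities will be tabulated and compared to published reports", and section 9.3 says "Frequency and type of recurrence (local, regional, distant) will be tabulated and compared to prior studies".

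**The concern.** The planned number of subjects is a basic fact of a protocol and should have one value throughout. Here the summary and the statistics section differ by a factor of two.

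The schema is what many readers consult for the size of the trial, for example in ethics review or accrual tracking. Someone who reads only that page would expect 50 subjects to be treated. They would not know that a further 50 are planned, or that the trial spans two versions of the eligibility criteria.

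What is at stake is the accuracy of the headline figure. The plan remains workable, because section 9.1 can be followed as it stands.

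**Working it through.** **Inputs**

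| Item | Value | Source |
|---|---|---|
| Stated sample size | 50 | Schema |
| First block | 25 | Section 9.1 |
| Second block, with running total | 25, total 50 | Section 9.1 |
| Block under revised eligibility | 50 | Section 9.1 |

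**Step 1: reproduce the plan's own figure.** First block + second block = 25 + 25 = 50. This agrees with the running total in section 9.1 and with the schema.

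**Step 2: add the third block.** 50 + 50 = 100. This does not agree with the schema. The difference is 100 − 50 = 50 subjects, and 50/100 = 0.50, so the schema figure is half of the enrolment that section 9.1 sets.

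**Step 3: does the third block add to the first two or replace them?** Section 9.1 calls the third block additional, immediately after closing the first two at 50. It therefore adds to them.

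**Step 4: what could the schema's 50 stand for?**

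- *Original enrolment (25 + 25).* The line was then not updated when section 9.1 was extended.
- *Revised-criteria cohort (50).* The line is then a cohort size shown without a label.
- *Whole trial.* This is excluded by step 2.

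The documents do not settle which of the first two applies. The number is the same under both, and neither the schema nor section 3.0 says which version of the criteria it presents.

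**Step 5: does anything else depend on the figure?** The plan states no alpha, power, target rate or margin, so no sample-size formula can be checked against either 50 or 100. The toxicity evaluation is tied to a count of 25 and does not change. Sections 9.2 and 9.3 describe tabulation and comparison with earlier reports, with no threshold that depends on the total.

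**The case against.** The strongest defence is that the schema describes only the cohort now being enrolled. A document revised in April 2008 may well show its current criteria, the schema prints one eligibility list with 50 beneath it, and section 9.1 assigns exactly 50 subjects to the new criteria. On that reading, 50 is a correct cohort size. It is also fair to say that a current protocol need only list current criteria, so the single list in section 3.0 is not a defect in itself.

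This is possible, but the documents do not say it. The schema carries the title of the whole trial and calls the number the sample size without qualification. If the defence is right, the line still needs a label and the total beside it.

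Two further objections stand. First, this is a mismatch between summary and body. It is not a miscalculation, since every sum inside section 9.1 is correct. Second, the harm is modest: the statistics section is the operative text and nothing in the analysis turns on the number. Both limit the weight of the point without removing it.

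**Conclusion.** The point holds: the schema's sample size is wrong as a statement of the trial total. The gap is 50 subjects, the schema showing 50 where section 9.1 adds up to 100. Confidence is high, because the result rests on addition and on reading the third block as additional, which is how section 9.1 words it. It does not depend on whether the figure was left over or is an unlabelled cohort size.

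The correction should be made, but the discrepancy does not threaten the design. No power, precision statement or decision rule in the plan changes.

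**What to change.** **Main change.** Replace the schema line with, for example: *Sample size: 100 patients (50 in the original enrolment, 50 under the 2008 revised eligibility criteria); see section 9.1.* If 50 was meant as the revised-criteria cohort, label it so and give the total of 100 beside it. The cost is one line, with no effect on design, analysis or procedures.

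**Optional, with low confidence.** Sections 9.2 and 9.3 could each add a sentence saying that toxicity and recurrence will be tabulated by eligibility cohort as well as combined. This does not follow from the mismatch. The superseded criteria are not in the document, so how far the cohorts differ cannot be judged from it. The eligibility version of each subject would have to be recorded, which section 9.4 does not mention.

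The separate cohort estimates would be less precise. At assumed event rates of 2%, 4% and 10%, exact (Clopper-Pearson) 95% intervals are 10.6, 13.2 and 18.5 percentage points wide with 50 subjects, against 6.8, 8.8 and 12.7 with 100. Because the combined table is kept, its precision is not lost.

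**Query only.** Section 9.1 cites a revision of April 4, 2008, while the document is dated April 8, 2008. A later revision can refer to an earlier one, so this is not an error. The sponsor could confirm both dates when correcting the schema.

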1.0 Introduction

General

Breast cancer is the most common site of cancer for women worldwide and has an enormous impact on the health of women. In the United States, approximately 210,000 new cases of breast cancer are estimated in 2003. Each year, approximately 40,000 women die of the disease, making it the second leading cause of cancer death in women.¹

Rationale for Whole Breast Irradiation

To date, there have been six large prospective randomized trials that have shown that the locoregional control and survival rates achieved with breast-conserving therapy are comparable to modified radical mastectomy in patients with early stage breast cancer.²⁻⁷ The major advantages of breast conserving therapy are reduced emotional/psychological trauma and superior cosmetic outcome. The disadvantage is that this involves a more complex, prolonged treatment requiring 5-7 weeks of external beam radiation therapy.

Rationale for Partial Breast Irradiation

The rationale for whole breast irradiation following lumpectomy is to reduce the breast recurrence rate by eliminating residual foci of cancer in the tumor bed and to treat presumed occult multicentric disease in remote areas of the breast. However, the majority (67-100%) of ipsilateral breast recurrences after breast conservation therapy are in the same quadrant of the initial tumor.⁸⁻¹¹ In fact, 80-90% of breast recurrences after breast conservation therapy occur in the immediate vicinity of the lumpectomy scar.^{10, 12} Upon review of multiple randomized trials and retrospective studies comparing lumpectomy alone versus lumpectomy and whole breast irradiation, it is apparent that there is no difference in remote breast recurrence (<4%).^{7,10,13,33}

NSABP B-06 analyzed 1851 patients with Stage I/II breast cancer randomized to total mastectomy, lumpectomy, or lumpectomy and whole breast irradiation. The breast recurrence rate in lumpectomy alone was 43% in contrast to a 10% breast failure rate for patients receiving lumpectomy and whole breast irradiation.¹³ The EORTC 22881/10882 Trial analyzed 5318 Stage I/II breast cancer patients who underwent lumpectomy with negative margins and axillary lymph node dissection, followed by 50 Gy to the whole breast. They were randomized to receive no boost versus a 16 Gy tumor bed boost. Local recurrence was 7.3% vs. 4.3% at 5 years (no boost versus boost), a 41% reduction in local recurrence.¹⁴ Thus it appears that delivering additional treatment to the tumor bed significantly reduces the chance of local tumor recurrence.

The next question that follows is if the whole breast irradiation can be eliminated altogether with delivery of a high dose of radiation limited only to the site at highest risk for recurrence. By confining treatment to a limited volume of breast tissue adjacent to the lumpectomy cavity, it may allow delivery of higher doses to high risk areas, potentially reducing acute and chronic toxicity, thus improving the quality of life in patients. In addition, the smaller target volumes may allow hypofractionated treatment schedules, which would decrease the time and inconvenience of breast conservation therapy,

eliminate scheduling problems with systemic chemotherapy, and potentially improve outcome by reducing delay to local therapy.

Trials Investigating Partial Breast Irradiation

Investigations of partial breast irradiation have, in fact, been performed, with excellent early results. Primarily Phase I, II and a few Phase III studies have been initiated using: high dose rate (HDR) brachytherapy, low dose rate (LDR) brachytherapy, external beam radiotherapy, and intra-operative radiotherapy.¹⁵⁻³² A hypofractionated treatment scheme has been used in all cases. Local recurrence rate has been <10% in all studies except two, which had poor selection criteria.^{25,26,29} When evaluated, cosmetic results have been rated Good/Excellent in >75% of the patients treated.

Phase I, II and III studies conducted at the National Institute of Oncology in Hungary have some of the longest follow-up data to date. Forty-five patients with T1 breast cancer were enrolled in the Phase I-II study and underwent lumpectomy followed by HDR brachytherapy 7 x 4.33 Gy or 7 x 5.2 Gy to the tumor bed. With a median follow-up of 57 months, the local recurrence rate was 4.4%. The 5-year probability of cancer-specific, relapse-free and local recurrence-free survival was 90.0%, 85.9%, and 95.6%, respectively. The phase III study was subsequently performed with an additional 126 patients randomized to receive 50 Gy WBRT or HDR brachytherapy 7 x 5.2 Gy to the tumor bed alone. With a median follow-up of 30 months, this study also confirms excellent locoregional tumor control of 100% in both arms. The 3-year probability of cancer-specific and relapse-free survival was essentially equivalent, 98.1% and 98.4% in the WBRT group and 100% and 94.4% in the HDR brachytherapy group.¹⁸

Several institutions have been evaluating accelerated partial breast irradiation using 3D conformal external beam radiotherapy.^{15,29,30} A concern of EBRT is that the breast is a moving target that may require larger volumes of normal breast tissue to be irradiated to avoid a geographic miss. William Beaumont Hospital has been studying this, with careful evaluation of breast motion using standard free-breathing virtual scans compared with CT scans obtained at the end of normal inhalation (NI) and exhalation (NE). They found that 5 mm of margin was sufficient to fully account for breast motion, with minimal use of immobilization devices (alpha cradle). Sixteen patients were treated using a CTV of 1.5 cm plus 1 cm for breathing motion/set-up uncertainty. A dose of 34-38.5 Gy was delivered in 10 fractions BID over 5 days using a 4-5 noncoplanar beam arrangement. With a median follow-up of 8 months, toxicity has been mild, consisting of mild fatigue, mild breast tenderness and mild to moderate erythema/dry desquamation.¹⁵ The RTOG also has a proposed Phase I/II protocol to evaluate 3D CRT confined to the lumpectomy site in Stage I/IIA breast carcinoma.

Rationale for Partial Breast Irradiation with Protons

Proton therapy has several advantages over other forms of radiotherapy for performing partial breast irradiation. Proton therapy would eliminate the additional surgical procedure required for brachytherapy. In addition, it is likely to improve dose homogeneity within the target volume, which may improve cosmetic results and reduce the risk of symptomatic fat necrosis associated with brachytherapy which has been reported to be as high as 40%. In comparison to three-dimensional conformal radiation therapy, the inherently superior depth dose characteristics (Bragg peak) would minimize the integral dose delivered to surrounding normal tissues, particularly the lung and heart. We anticipate that this will result in decreased toxicity and less risk of radiation induced malignancy.

2.0 Objectives

- 2.1 To evaluate the technical feasibility of delivering partial breast irradiation with proton beam.
- 2.2 To evaluate the acute and long term toxicity associated with partial breast proton therapy.
- 2.3 To evaluate the cosmetic results with partial breast proton therapy
- 2.4 To determine the local tumor control and survival associated with partial breast proton therapy.

3.0 Eligibility Criteria

- 3.1 Histologic evidence of invasive carcinoma (except lobular carcinoma) or ductal carcinoma-in-situ.
- 3.2 Primary tumor < or = 3 cm.
- 3.3 AJCC stage 0, I, or II
- 3.4 Patients with invasive carcinoma must have an axillary node dissection or sentinel lymph node biopsy. If the sentinel node is positive an axillary node dissection must be performed. A minimum of 6 nodes must be pathologically reviewed. No more than 3 nodes may contain metastatic carcinoma and there can be no evidence of extra-capsular extension. Axillary staging is not required for DCIS.
- 3.5 Surgical clips will be placed outlining margins of lumpectomy cavity.

- 3.6 Lumpectomy margins negative by at least 2 mm and/or negative reexcision
- 3.7 No evidence of distant metastasis.
- 3.8 No evidence of extensive intraductal component.
- 3.9 No patients with multicentric ipsilateral carcinoma or contralateral carcinoma.
- 3.10 No prior radiation therapy to the breast or chest wall.
- 3.11 No prior malignancy except non-melanoma skin cancer unless disease free for > 5 years.
- 3.12 No patients who are pregnant or lactating.
- 3.13 No patients with history of collagen vascular disease.
- 3.14 No prior chemotherapy for breast cancer

4.0 Pretreatment Evaluation

- 4.1 History and physical examination.
- 4.2 Bilateral mammogram.
- 4.3 Chest x-ray.
- 4.4 CBC and serum chemistries with liver function tests.
- 4.5 Bone scan if alk phos is elevated or if there are symptoms of bone metastasis
- 4.6 Abdominal CT if liver function test are abnormal.
- 4.7 Breast MRI (optional)

5.0 Radiation Therapy

- 5.1 Radiation therapy will start within 4 weeks of surgical resection
- 5.2 Immobilization and treatment planning CT scan of the chest.
- 5.3 Treatment Planning
 - 5.3.1 Outline tumor bed using surgical clips and clinical information
 - 5.3.2 Add 1 cm in all directions to create clinical target volume (CTV) excluding chest wall and skin.
 - 5.3.3 Create multi-field treatment plan with the 90% isodose covering the CTV while the skin surface receives no more than 70%.

5.4 Dose, Fractionation and Treatment

- 5.4.1 40 CGE will be delivered to the CTV in 10 equal fractions over ten treatments days.
- 5.4.2 At least 2 fields will be treated each day.
- 5.4.3 Orthogonal localization radiographs to be taken prior to each treatment with surgical clips used as localizing markers.

6.0 Surgical Therapy

- 6.1 Excisional biopsy (lumpectomy) will be done per established surgical standards. Surgical clips will be placed to outline the surgical cavity (i.e. deep, superior, inferior, right, left).
- 6.2 Axillary lymph node sampling or sentinel lymph node biopsy will be done per surgeon's preference.

7.0 Systemic Therapy

- 7.1 Chemotherapy and/or hormonal therapy may be given following the completion of proton therapy as recommended by the treating oncologist.

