8.0 Patient Assessments

8.1

Study Parameters

Assessment	Pre TX	1 Mo Post TX	6 MO Post TX then every 6 months	6 MO Post TX then annually
H & P	X	X	X*	
Disease Status	X	X	X*	
Toxicity Assessment	X	X	X*	
Mammo	X			X
CBC & LFT	X	As indicated	As indicated	As indicated
Bone scan or CT scan	As needed	As indicated	As indicated	As indicated
Photos	X			X
Cosmesis Assess. (MD&Pt.)			X	X
Chest X-ray	X			X

* Until year 5 at which time complete assessment will be conducted annually

8.2

Definitions for Cosmetic Outcomes

Cosmetic outcome will be graded by the study subject, radiation oncologist, and surgical oncologist periodically following treatment according to section 8.1. The grading scale will be as follows:

Excellent – the treated breast, when compared to the untreated breast, shows minimal or no changes in shape or size. There may be minimal subcutaneous fibrosis or scarring.

Good – there are mild changes in the size and shape of the treated breast. Scarring within the breast causes mild alterations

in breast shape.

Fair – there is a clear difference in the size and/or shape of the treated breast that involves $\frac{1}{4}$ or less of the treated breast.

Poor – marked changes in the treated breast that involves more than $\frac{1}{4}$ of the breast.

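### The 1-month acute toxicity table can include chemotherapy effects, because systemic therapy may start once protons end and the plan neither schedules its recording nor separates it

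*Combined protocol and SAP*

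**What the plan says.** On timing, section 7.1 states: "Chemotherapy and/or hormonal therapy may be given following the completion of proton therapy as recommended by the treating oncologist". The schema gives the same discretion without any timing: "Chemotherapy and/or hormonal therapy as needed per treating oncologist". Neither place gives a minimum interval, a regimen or a duration. Eligibility criterion 3.14 reads "No prior chemotherapy for breast cancer".

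On data, the section 8.1 schedule has nine rows: history and physical, disease status, toxicity, mammogram, blood count and liver tests, bone or CT scan, photographs, cosmesis and chest X-ray. The row "Toxicity Assessment" is marked before treatment, at 1 month, at 6 months and then every 6 months until year 5, after which assessment is annual. No row covers systemic or concomitant therapy.

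On analysis, section 9.2 states: "All acute toxicities will be scored according to the NCI Common Toxicity Criteria v2.0". Late toxicity goes on the RTOG scale. Toxicities of grade 3 or above are reported as adverse events, and frequencies are tabulated and set against published reports. Section 9.1 makes the second 25 subjects depend on a toxicity evaluation judged acceptable, then adds 50 subjects under the 2008 revision.

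The objective served is 2.2: "To evaluate the acute and long term toxicity associated with partial breast proton therapy".

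**The concern.** The trial has one arm, so its toxicity frequencies can be interpreted only against outside reports. No control group receives the same systemic therapy without protons. If some patients have begun chemotherapy by the 1-month visit, their nausea, fatigue or low blood counts enter the same table as radiation effects.

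Two uses of that table are at stake. The first is the comparison with published reports in 9.2, where an excess could be read as a proton effect. The second is the enrolment decision in 9.1, which has neither a numeric limit nor an attribution rule. The pre-treatment toxicity assessment does not solve this, because the exposure begins after it.

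**Working it through.** The plan states no toxicity rate, target or expected share on systemic therapy, so there is no figure of its own to reproduce. The main check is to set the sections side by side.

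**1. When can chemotherapy occur?** Section 3.14 rules it out before enrolment, and 7.1 places it after protons with no minimum gap. It can therefore begin between the last fraction and the 1-month assessment.

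**2. Is it recorded?** None of the nine rows in 8.1 asks for it. A history is taken at each toxicity visit, and section 9.4 refers to treatment records in general terms. Either might capture systemic therapy, but neither specifies type or dates.

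**3. Is it separated?** Section 9.2 covers all acute toxicities, and nothing in 9.1 or 9.2 attributes or groups them.

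**4. Will use vary between patients?** Probably. DCIS is eligible, and so is node-positive disease: "No more than 3 nodes may contain metastatic carcinoma and there can be no evidence of extra-capsular extension". This rests on the current criteria; those that applied to the first 50 subjects are not shown.

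**5. Which events are exposed?** The 3D-conformal series in section 1.0 reported fatigue, breast tenderness, and erythema or dry desquamation. Of these, fatigue is the obvious overlap with chemotherapy; the others are local. Blood count and liver tests after treatment are done only as indicated in 8.1. Patients on chemotherapy are likely to be tested more often (an inference), which would add laboratory toxicities.

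**6. How could the size behave?** All inputs here are assumed. Let p be the rate of any grade 3+ toxicity with protons alone, f the share who have started chemotherapy, and q the rate of grade 3+ toxicity caused by chemotherapy, taken as independent.

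Pooled rate = p + f × q × (1 − p)

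| p | f | q | Pooled rate | Expected in 25 | Protons alone in 25 |
|---|---|---|---|---|---|
| 2% | 20% | 10% | 0.02 + 0.2 × 0.1 × 0.98 = 4.0% | 1.0 | 0.5 |
| 2% | 60% | 40% | 0.02 + 0.6 × 0.4 × 0.98 = 25.5% | 6.4 | 0.5 |

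With p = 5% the corresponding range is 6.9% to 27.8%. The width reflects the assumptions on f and q. It also describes a composite of any grade 3+ event, which 9.2 does not say it will tabulate. It shows how the result depends on f, a quantity the plan does not schedule for collection; it is not an estimate for this trial.

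**7. Does the point extend to recurrence (9.3)?** Let r be recurrence without systemic therapy, s the share treated and h an assumed hazard ratio.

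Pooled recurrence = (1 − s) × r + s × (1 − (1 − r)^h)

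Take r = 4.4% (the brachytherapy series in section 1.0), with s from 30% to 90% and h from 0.5 to 0.7, both assumed.

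- s = 90%, h = 0.5: 0.1 × 4.4% + 0.9 × (1 − 0.956^0.5) = 2.4%, or 1.2 events in 50.
- s = 30%, h = 0.7: 0.7 × 4.4% + 0.3 × (1 − 0.956^0.7) = 4.0%, or 2.0 events in 50.

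Without systemic therapy 50 × 4.4% = 2.2 events are expected, so the shift is 0.2 to 1.0 events. With r = 7.3% (the no-boost arm cited in section 1.0) the range is 4.1% to 6.7%, or 2.0 to 3.3 events against 3.65. For scale, 2 events in 50 has an exact 95% interval of about 0.5% to 13.7%.

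**The case against.** The strongest reply is that the plan is silent on attribution, which differs from assigning every event to protons. A reader might infer that chemotherapy toxicity will in fact be counted as a proton result. The documents do not say so: the investigators could ask about treatment at the history visits, consult the records and judge cause. This stands against the stronger statement. It does not supply planned recording, dates or a split.

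A second reply is that toxicity frequencies are most naturally tabulated by event type, so a low blood count would not raise the frequency of breast erythema. This also stands. It limits the problem mainly to systemic, laboratory and fatigue rows, and rules out quoting one inflated overall percentage.

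A third concerns 6 months. Late toxicity is scored on the RTOG scale and the plan gives no acute/late boundary, so the scale in use at that visit is unknown. The argument is secure at 1 month only.

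Finally, a reader might infer from objective 2.4, "To determine the local tumor control and survival associated with partial breast proton therapy", that systemic therapy biases the recurrence comparison in 9.3 in favour of protons. The documents do not support this. Bias requires systemic therapy use to differ from that in the prior studies, and neither mix is given. The direction is open too, since oncologists may treat the higher-risk patients. The illustrative shift is well inside sampling error.

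**Conclusion.** The point holds for acute toxicity at 1 month and for any 9.1 toxicity evaluation that draws on the same data. Followed as written, the plan can mix chemotherapy effects into these results and provides no means of separating them from the proton effects in objective 2.2. This rests on the text of 3.14, 7.1, 8.1, 9.1 and 9.2, and on the assumption that some patients begin chemotherapy before the 1-month visit, which 7.1 permits.

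The size is not computable from the documents. It is zero if nobody has started chemotherapy by then, and it grows with the share who have. Local breast events should be little affected. No claim of biased recurrence is made. The change is worth making because it is cheap, and because without it an excess of systemic acute toxicity could not be interpreted.

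**What to change.** - **8.1:** add an item recording chemotherapy and hormonal therapy (type, start and stop dates) at each visit.
- **9.2:** tabulate acute toxicity by event type, separately for patients who had and had not started chemotherapy by that visit. Show local breast and chest-wall events for all patients as well.
- **9.1:** use the same split in any toxicity evaluation.
- **Comparison with published reports:** state systemic therapy use in this trial and, where reported, in the comparison series. Restricting the comparison to patients without chemotherapy could be less like-for-like if the published series included patients who received it.
- **9.3:** report the proportion receiving systemic therapy beside the recurrence table, as context only. A split by treatment received is confounded by indication and would not isolate a proton effect.

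The cost is one data item and one table split, with no change to treatment. The subgroups will be small and descriptive. For patients already enrolled, dates would have to be retrieved from oncology records, and some may be missing.
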